## Statistical Analysis Plan

**Sponsor:** Island Pharmaceuticals Ltd  
**Protocol Number:** ISLA101-P01-CT001

the derivation of the baseline values. Results including, but not limited to, 'Not done', 'Not applicable', 'Unknown' will not be included in the baseline derivations.

Baseline calculation for the ECG parameters will be based on the mean value of the triplicate ECG reading at baseline visit for Cohort 1-3.

- **Change from Baseline:** The change from baseline value is defined as the difference between the result collected/derived at a post-baseline visit and the baseline value (for that specific period for changes from the baseline values).

The change from baseline value at each post-baseline visit will be calculated for all continuous parameters using the following formula:

$$\text{Change from Baseline Value} = \text{Result at Post-Baseline Visit} - \text{Baseline Value}$$

The change from baseline value will only be calculated if the specific post-baseline result and the baseline value for the parameter are both available and will be treated as missing otherwise. In the data listings, the change values will be set to '-' (not applicable) for pre-baseline assessments.

- **Study Day:** The study day of an event is defined as the relative day of the event starting with the date of the first study drug administration (reference date) as Day 1 (there will be no Day 0).

The study day of events occurring before the study drug administration will be calculated as:

$$\text{Study Day} = (\text{Date of Event} - \text{Date of Study Drug Administration})$$

For events occurring on or after Day 1, study day will be calculated as:

$$\text{Study Day} = (\text{Date of Event} - \text{Date of Study Drug Administration}) + 1$$

Study days will only be calculated for events with complete dates and will be undefined otherwise.

### 5.1.3 Default Descriptive Statistics and Data Presentation Rules

Unless otherwise stated, summary statistics including the number of subjects, mean, standard deviation, median, minimum, and maximum, will be presented for all continuous variables. Minimum and maximum values will be presented to the same decimal precision as the raw values, the mean and median values to one more and the standard deviation values to two more than the raw values. Derived values (including descriptive statistics) will be presented to a maximum of 4 significant decimals.

For categorical variables, per category, the absolute counts (n) and percentages (%) of subjects with data, and if appropriate, the number of subjects with missing data, will be presented. Unless specifically stated otherwise, denominator for all percentage calculations will be the number of subjects in the specific treatment group and analysis set. All percentages will be presented to one decimal place except for 100%. Where a count is zero, the percentage will not be shown (e.g., 0 (0.0%) will be displayed as 0).

If required, results will be rounded using the SAS® function ROUND. Values will be rounded after all calculations have been performed.

### 5.1.4 Date and Time Display Conventions

The following display conventions will be applied in all outputs where dates and/or times are displayed:

- Date only: YYYY-MM-DD
- Date and time: YYYY-MM-DD HH:MM

If only partial information is available, unknown components of the date or time will not be presented, for example if only the year is known, '2016'. Times will be reported using a 24-hour clock.

**Statistical Analysis Plan**

**Sponsor:** Island Pharmaceuticals Ltd  
**Protocol Number:** ISLA101-P01-CT001

**5.1.5 General Display Conventions**

All data collected during the study (data originating from the eCRFs or electronic transfers), except for screen failure data, will be presented in the data listings. Event-based listings will be sorted by cohort, treatment group, subject number and event start and end dates. Assessment-based listings will be sorted by cohort, treatment group, subject number, parameter name (alphabetically unless specifically stated otherwise), visit and time point (if applicable).

Fields that are missing because they are not applicable for the subject/time point (for example change from baseline results at the baseline visit) will be presented as “-”, unless otherwise specified. Missing data points will be presented as blank fields in the data listings.

All summary tables will be presented by the treatment group. Assessment-based tables will be sorted alphabetically by parameter (unless specifically stated otherwise) and chronologically by visits/time point within parameter. Only values collected at scheduled study visits/time points will be presented in summary tables. Event-based tables will be ordered as specified in Section 6.

Treatment groups will be presented based on increasing dose levels of ISLA101 followed by a pooled Placebo groups and an All-Subjects group (only for the baseline tables).

Tables 5,6, and 7 present the treatment group, and visit labels that will be used in the tables, listings, and figures (TLFs).

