#### 8.1.5 Unscheduled Assessments

If a subject reports any AE(s) that present cause for concern during the study, they may be asked to complete further assessments. Any other procedures necessary to monitor the AE may be performed at the Investigator's discretion.

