#### 8.2.3 Clinical Laboratory Assessments

Standard clinical laboratory profiles for serum chemistry, hematology, and urinalysis will be evaluated. Specific laboratory tests to be performed at each study visit are described in Section 8.1.

All clinically significant laboratory abnormalities beginning with Day 1 must be recorded as an AE in the subject's source documents and on the appropriate CRF. A clinically significant laboratory abnormality that has been verified by retesting will be followed until the abnormality returns to an acceptable level or a satisfactory explanation has been obtained.

Tests for hepatitis B surface antigen, hepatitis C virus antibodies, and HIV will be completed at screening to determine eligibility.

A UDS, an alcohol breath test, and a urine cotinine test or breath CO test will be performed at screening. An alcohol breath test and urine cotinine or breath CO test will be performed at Day -1.

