**5.1.2 Definitions**

The following definitions will be used:

- **Date of the First Study Drug Administration:** The date of the first study drug administration is defined as the earliest date on which study drug was administered as reported on the 'Study Drug Administration' eCRF.
- **Baseline:** The baseline value is defined as the last available valid assessment collected prior to the first study drug administration. Repeat and unscheduled assessments will be included in

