### 6.8.3 Laboratory Parameters

The laboratory parameters described in Section 4.1.3 will be summarized and listed.

The summary tables of hematology, coagulation and biochemistry results will present summary statistics for each laboratory parameter within the specific test panel by treatment group. For each parameter, summaries will be presented for the baseline and each scheduled post-baseline visit. In addition, summaries will be presented for the change from baseline values at each scheduled post-baseline visit. Refer to Section 4.1.3 for the handling of character results.

The summary of hematology, coagulation, and biochemistry shift tables will present summaries for the shifts in the result classifications ('Normal', 'Low', 'High') from the baseline to each of the scheduled post-baseline visit for each parameter with a defined reference range, within the specific test panel.

The listings of hematology, coagulation and biochemistry data will include all laboratory data (collected at scheduled and unscheduled visits) in the clinical database. The listings will present all the information (fields) that is available in the laboratory dataset. In addition, the observation that was used as the baseline records (values) for each parameter will be flagged, the change from baseline value and the derived result classification (based on the normal ranges where applicable) at each post-baseline visit will be presented.

The summary of urinalysis table will present the number and percentage of subjects for each of the result classifications (Normal, Abnormal NCS and Abnormal CS) for the baseline, each scheduled post-baseline per parameter.

The listing of urinalysis (including microscopy) data will include all laboratory data (collected at scheduled and unscheduled visits) in the clinical database. The listings will present all the information (fields) that is available in the laboratory dataset. In addition, the observation that was used as the baseline record (value) for each parameter will be flagged.

The FSH parameters will be listed as part of the pregnancy listing.

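### A laboratory abnormality seen only at an unscheduled assessment is missing from the shift tables, and an unscheduled vital-sign or ECG extreme is missing from the by-visit summaries, because the SAP has no worst-post-baseline row

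*SAP*

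**What the plan says.** **Display rule.** SAP 5.1.5 reads "Only values collected at scheduled study visits/time points will be presented in summary tables", with no exception. Table 7 of the SAP gives unscheduled visits a label for listings and leaves their summary-table label blank. SAP 5.7 declares windowing not applicable, so no rule moves an unscheduled value into a scheduled visit.

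**Baseline.** SAP 5.1.2 says "The baseline value is defined as the last available valid assessment collected prior to the first study drug administration". Under the same definition, pre-dose repeats and results obtained outside the schedule count towards that value.

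**Laboratory shift tables.** SAP 6.8.3 plans these for the three blood panels only, using the classes Low, Normal and High. Each comparison runs "from the baseline to each of the scheduled post-baseline visit for each parameter with a defined reference range". The shells show Days 1, 2, 3, 4, 5 and follow-up.

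**Vital signs and ECG.** SAP 6.8.4 and 6.8.5 give summary statistics by scheduled visit. ECG also has counts of the overall assessment. Neither has a shift table.

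**Listings.** SAP 6.8.3 to 6.8.5 put unscheduled laboratory, vital-sign and ECG results in the listings. Blood-test results carry their change from baseline and range class.

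**Unscheduled assessments are expected.** Protocol 8.1.5 says "If a subject reports any AE(s) that present cause for concern during the study, they may be asked to complete further assessments". On abnormal blood tests, protocol 8.2.3 says "A clinically significant laboratory abnormality that has been verified by retesting will be followed until the abnormality returns to an acceptable level". Protocol 8.3 allows about 25 mL of blood for two repeat laboratory assessments, and protocol 3.1 lets confinement run past Day 5 for safety.

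**The concern.** Clinical laboratory tests and vital signs are named primary endpoints, and the safety analysis is descriptive only (SAP 6.8). The by-dose tables are therefore the main comparative statement that the report will make about them.

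Unscheduled assessments are not a random sample of time points. They are ordered because something looks wrong, or because a subject is kept in or called back. A display rule that drops all of them will, when it matters, drop values from the subjects with a problem. If a result leaves the reference range only at such an assessment, the shift table for that dose shows no change, and a reader comparing dose columns has no sign that the listing says otherwise.

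**Working it through.** The plan states no figure on this point, so there is nothing to reproduce. The check takes each way an extreme value can arise and asks which outputs would show it.

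**Inputs**
- Scheduled laboratory and vital-sign assessments after check-in: Days 1, 2, 3, 4, 5 and 8 (±1) for Cohorts 1 to 3, with Days 10 to 14 and 17 (±1) for the fed period (schedule of assessments).
- Scheduled post-dose ECG: one time point per period, 5 hours after dosing.
- Group size: 6 active subjects per dose; 2 placebo per cohort, pooled to 6 across Cohorts 1 to 3.

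**Cases**
1. *Abnormality found at a scheduled visit, then retested.* The value that prompted the retest is in the shift table. Only the retest is left out.
2. *Retest worse than its trigger.* The retest value is not tabulated. The shift classes are only Low, Normal and High, so if the trigger was already High the class is shown, and what goes missing is the size of the rise. If the trigger was still within range, the class goes missing too.
3. *Abnormality seen only at an unscheduled draw*, for example between Day 5 and Day 8, or after follow-up. It is in no by-visit summary and no shift table. It appears in the listing and, if reported as an adverse event, in the TEAE tables.
4. *Unscheduled vital-sign or ECG extreme.* There is no shift table to miss, but the value is absent from the by-visit means, minima and maxima. For ECG, any tracing beyond the single 5-hour time point falls here.

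**Is the adverse-event route a substitute?** Protocol 8.2.3 requires every clinically significant laboratory abnormality from Day 1 onward to be recorded as an adverse event. Protocol 9.1.1 is narrower: it requires this for significant laboratory or vital-sign shifts when they cause symptoms, need treatment or consultation, or lead to discontinuation of study drug. Under either section, an out-of-range value judged not clinically significant need not become an adverse event, yet a shift table would count it. Events of special interest are flagged in the adverse-event listing, but Attachment 1 contains no summary table of them.

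**Size, as a hypothetical illustration.** Take one subject in an active group of 6 whose ALT is normal at every scheduled visit and High at an unscheduled Day 6 draw. All six post-baseline rows show Normal to Normal.
- As planned: 0/6 = 0%.
- With a worst-post-baseline row: 1/6 = 16.7%.

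This assumes that all six subjects have baseline and post-baseline results, since the shells base percentages on subjects with both. In the fasted-versus-fed tables each placebo column holds 2 subjects, so one subject there weighs 1/2 = 50 points.

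**Internal conflict.** Read literally, SAP 5.1.5 also bars an unscheduled pre-dose value from the Baseline row, although SAP 5.1.2 can make that value the baseline.

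**The case against.** The strongest case on the other side is that little is lost. Scheduled-only by-visit tables are a deliberate and common convention. Laboratory tests are scheduled on Days 1 to 5 and 8, so the gap in the calendar is short. An unscheduled visit usually follows an adverse event that is already recorded and tabulated. With about 24 subjects the listings can be read in full. Escalation does not depend on these tables, because the Safety Review Committee reviews all available data up to 96 hours. The illustration is hypothetical, and the true effect may be zero.

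Most of this stands, and it limits the point to how results are reported. It does not close the gap. A listing is not a comparison by dose, and the adverse-event route is incomplete for the reasons shown in the working.

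A reader might also infer three stronger things that the documents do not support.
- *That the value prompting a retest never reaches the shift tables.* Protocol 8.2.3 has the retest follow the abnormality. A trigger found at a scheduled visit is tabulated.
- *That vital-sign and ECG results drop out of shift tables.* None are planned for them; the loss is from the by-visit summaries.
- *That letting unscheduled values set the baseline hides harm.* If a normal repeat replaces an abnormal baseline, a later High is shown as Normal to High instead of High to High, which is more visible. An abnormal repeat would act the other way. The direction is not fixed.

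**Conclusion.** The point holds for extremes seen only at an unscheduled assessment. For laboratory data, an abnormal class seen only there is absent from the shift tables. For vital signs and ECG, the value is absent from the by-visit summaries. It does not hold for abnormalities first found at a scheduled visit.

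The documents do not say how often such values will occur. The effect is zero if there are none, and otherwise 16.7 percentage points per affected subject in a group of 6 with complete data. No error rate, sample size or escalation decision is affected. The change is worth making as a cheap improvement to the reporting of primary endpoints.

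**What to change.** 1. Keep all by-visit statistics on scheduled values.
2. Add a row, *Worst post-baseline (scheduled and unscheduled)*, by period, to shift Tables 14.3.4.1.2.x, 14.3.4.2.2.x and 14.3.4.3.2.x. Classify worst-low and worst-high separately, so that a subject with both is counted in each.
3. Add post-baseline minimum and maximum rows, including unscheduled values, to Tables 14.3.5.x and 14.3.6.1.x. The same rows in the laboratory summary tables would be an optional extra; they would show the size of a retest that is worse than its trigger.
4. Amend SAP 5.1.5 to exempt these rows and the Baseline row, which also removes the conflict with SAP 5.1.2.
5. While editing, state which value the by-visit tables use when a post-dose test is repeated at the same scheduled visit. The SAP does not say.

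**Cost.** The core change touches 10 table shells: 3 laboratory panels × 2 tables, plus 2 vital-sign and 2 ECG tables. It needs a direction rule for each parameter, a few derived records, and a rule assigning unscheduled values between the Day 8 visit and the fed dose to a period. No new data are needed: the values are already planned for the listings, and the blood tests already carry a range class.

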**Table 5 Study Treatments – Tables and Figures**

Cohort: Actual Treatment	Treatment Label
Cohort 1: ISLA101 300 mg Fasted	ISLA101 300 mg Fasted
Cohort 2: ISLA101 600 mg Fasted	ISLA101 600 mg Fasted
Cohort 3: ISLA101 900 mg Fasted	ISLA101 900 mg Fasted
Cohort 4: ISLA101 TBD* mg Fed	ISLA101 TBD* mg Fed
Cohort x/4: ISLA101 TBD* mg	ISLA101 TBD* mg Fasted/Fed
Cohort 1-3: Placebo	Pooled Placebo
Cohort 4: Placebo (Fasted)	Placebo (Fasted)
Cohort 4: Placebo (Fed)	Placebo (Fed)
Cohort 1-3	All Subjects

\*One of the Cohort 1 to 3 Subjects (the highest tolerated dose-level cohort) will return for additional dose to determine the effect of food. Subjects participating in Cohort 4, the food effect cohort, will maintain the same treatment assignment from their fasted cohort.

**Table 6 Study Treatments – Listings**

Cohort: Actual Treatment	Treatment Label
Cohort 1: ISLA101 300 mg Fasted	Cohort 1: ISLA101 300 mg Fasted
Cohort 1: Placebo	Cohort 1: Placebo Fasted
Cohort 2: ISLA101 600 mg Fasted	Cohort 2: ISLA101 600 mg Fasted
Cohort 2: Placebo	Cohort 2: Placebo Fasted
Cohort 3: ISLA101 900 mg Fasted	Cohort 3: ISLA101 900 mg Fasted
Cohort 3: Placebo	Cohort 3: Placebo Fasted
Cohort 4: ISLA101 TBD* mg Fed	Cohort 4: ISLA101 TBD* mg Fed
Cohort 4: Placebo	Cohort 4: Placebo Fed

\*One of the Cohort 1 to 3 Subjects (the highest tolerated dose-level cohort) will return for additional dose to determine the effect of food.

**Statistical Analysis Plan**

**Sponsor:** Island Pharmaceuticals Ltd  
**Protocol Number:** ISLA101-P01-CT001

**Table 7 Study Visits**

Actual Visit	Summary Table Treatment Label	By-subject Listing Treatment Label
Screening		Screening
Day -1 – Clinic Check-In	Baseline	Day -1
Day 9 -Clinic Check-In		Day 9
Day 1	Day 1	Day 1
Day 10		Day 10
Day 2	Day 2	Day 2
Day 11		Day 11
Day 3	Day 3	Day 3
Day 12		Day 12
Day 4	Day 4	Day 4
Day 13		Day 13
Day 5 - Discharge	Day 5	Day 5
Day 14 - Discharge		Day 14
Day 8 – Follow Up/ET	Follow-up	Day 8 – Follow UP
Day 17 – Follow Up/ET		Day 17 – Follow Up
Unscheduled		Unscheduled
		Early Termination*

\*If early termination occurred, the visit labels “Day 8 – Follow Up” and “Day 17 – Follow Up” will be marked as “Early Termination”.

**5.2 Hypotheses and Decision Rules**

Not applicable for this study.

**5.3 Multiple Comparisons and Adjustments for Multiplicity**

Not applicable for this study.

**5.4 Covariates**

Not applicable for this study.

**5.5 Multi-Centre Data**

Not applicable for this study.

**5.6 Handling of Missing Data****5.6.1 Efficacy Endpoints**

Not applicable for this study.

**5.6.2 Safety Endpoints**

Missing start dates/times will be imputed to one minute after the study drug administration.

Partial start dates will be imputed to the last day of the month/year considering that the start date should not be after the stop date/time. Missing start times will be imputed to '23:59'. If the imputation results in the start date/time being after the stop date/time, the start date/time will be set to the stop/date time.

**Statistical Analysis Plan**

**Sponsor:** Island Pharmaceuticals Ltd  
**Protocol Number:** ISLA101-P01-CT001

The imputation method will only be used to determine treatment emergence and to determine the time of the event relative to the first administration of study drug. If no clear determination can be made, the event will be deemed to have started at the same time as the study drug, i.e., the event will be analyzed as being treatment emergent.

Stop dates/times will not be imputed if the AE is ongoing.

A worst-case approach will be followed in the event of missing severity or causality data. If the severity is missing, 'Severe' will be imputed. If causality data are missing, 'Definitely Related' will be imputed.

Missing/partial concomitant medication dates will be handled in a similar fashion as described for the adverse event dates.

## **5.7 Windowing Conventions**

Not applicable.

## **5.8 Interim Analyses**

No interim analyses are planned for this study.

## **5.9 Clinical Data Interchange Standards Consortium (CDISC) Specifications**

The study data will be converted into CDISC-compliant datasets based on the Study Data Tabulation Model Implementation Guide (SDTMIG) Version 3.3 and the Analysis Data Model Implementation Guide (ADaMIG) Version 1.1.

The SDTM data package will be based on raw data (clinical database and external data) and will include SAS® datasets and transport files (.XPT format) for each required SDTM domain, as well as the SDTM Case Report Tabulation Data Definition Specifications (CRT-DD) (define.xml Version 2.1) that describes the origin of the data and all the derivations and imputations that were applied, and includes an SDTM-annotated CRF and the Study Data Reviewer's Guide (SDRG).

The ADaM datasets will be based on the SDTM datasets and will be used for the analysis. The ADaM data package will include SAS® datasets and transport files (.XPT format) for each analysis dataset, as well as the ADaM CRT-DD (define.xml Version 2.1) and the Analysis Data Reviewer's Guide (ADRG).

The SDTM and ADaM data packages will be validated using Pinnacle 21 Community ([name]) and the validation reports will be included with the respective data packages.

All data conversions will be performed using SAS® Version 9.4 or higher (SAS Institute, Cary, North Carolina, USA) with program code prepared specifically for the study.

The output SAS® programs will generate rich-text-formatted (RTF) output with the ".RTF" extension using the SAS® Output Delivery System (ODS). Each output display will show the name of the SAS® program which was used to produce it.

## **6. Statistical Analyses**

The baseline cohort 1 to 4 results will be presented in the same outputs. Furthermore, the results from the highest tolerated dose-level cohort (fasted results) in one of Cohort 1 to Cohort 3 will be presented with the results of Cohort 4 (fed results) (where appropriate).

Summary tables and analyses will be based on the specified analysis population in each section. Data listings will be based on the Safety Population unless specifically stated otherwise.

